Resourcefulness is an “acquired repertoire of skills and behaviors necessary for the successful execution of self-control behavior.”^{19 p.26} These skills are learned throughout life by informal training or may be taught in cognitive behavioral programs and include the belief that one is able to cope effectively despite adversity.¹⁹ Skills of self-instruction, problem-solving, belief in coping effectiveness are used to control the effects of disturbing feelings, thoughts and sensations on performance of daily tasks.¹⁹ Zauszniewski’s²⁰ model includes personal resourcefulness (self-help) and social resourcefulness (help-seeking) that are beneficial for maintaining healthy physical and psychological functioning across the lifespan. Resourcefulness training (RT) includes teaching positive self-talk, problem-solving and priority setting.¹⁵

Empirical evidence indicates that resourcefulness is a significant predictor of quality of life for non-caregivers/caregivers.^{19, 23} **Parent outcomes** are conceptualized as absence of depressive symptoms, positive family functioning, better self-assessed health. **Depressive symptoms** include depressed mood and feelings of helplessness and hopelessness.¹⁰ Greater resourcefulness is a significant predictor of a decreased level of depressive symptoms.²⁵ Conversely, less resourcefulness contributed to perceptions of worse family functioning in grandmothers raising grandchildren.¹⁷ **Family functioning** is a parent’s perception and level of satisfaction with relationships between the family and individuals as well as subsystems and the community. **Self-assessed health** is the mother’s perception of her health and includes both physical and psychological well-being.²⁷ Based on the theoretical and empirical literature, the study model proposes that contextual factors, process regulators, and resourcefulness all directly affect quality of life outcomes.

Inclusion and Exclusion Criteria

1. Describe how individuals will be screened for eligibility.
2. Describe the criteria that define who will be **included** in your final study sample.

	Inclusion
1.	Parents who are at least 18 years of age
2.	Parents caring for a child age 16 years and younger at home who is technology-dependent (Group 1 mechanical ventilators; Group 2 intravenous nutrition/medication; Group 3 respiratory or nutritional support);
3.	Able to speak, write and understand English.
4.	

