3. Describe the criteria that define who will be **excluded** in your final study sample.

	Exclusion
1.	Parents of children with cancer.
2.	
3.	
4.	

Number of Research Participants

1. *Indicate the target number of research participants to be accrued locally.*
2. *If this is a multi-site study, indicate the total number of research participants to be accrued across all sites.*

For this study, 123 subjects are expected to be enrolled.

Vulnerable Populations

1. *Indicate specifically if you will include each of the following special populations by checking the appropriate box:*

- Adults unable to consent**
- Minors (infants, children, teenagers)**
 - Wards of the state
 - Foster Children
- Pregnant Women**
- Neonates**
- Neonates of Uncertain Viability**
- Employees of CWRU or UHHS**
- Prisoners**
- Illiterate Individuals**
- Non-English Speaking**
- University Students**

2. *If the research involves individuals that are included in a vulnerable population, describe the additional safeguards included to protect the rights and welfare of the individuals for each population indicated.*

We will include pregnant women or women who become pregnant while enrolled in the study because many mothers of technology-dependent children are in the child-bearing years. They will be told that they are volunteers and can leave the study at any time. While we will not be directly asking the children any questions we will be asking their parent to describe things such as what type of technological equipment they use and questions about their eating and sleeping. Therefore, we have a procedure for asking about the child's assent if they are 7 years or older.

3. *If excluding pregnant women, illiterate or non-English speaking individuals, provide a scientific rationale for the exclusion. Inconvenience or cost is not an acceptable rationale.*

We will exclude illiterate or non-English speaking individuals due to the amount of reading, writing that must be done as part of the intervention and follow up data collection. Also, our instruments have not been translated into another language.

Recruitment Methods

1. *Describe the source of the research participants.*
2. *Describe the methods that will be used to identify potential research participants.*

3. *Justify the feasibility of recruiting the required number of suitable research participants within the agreed recruitment period. For example, how many potential research participants do you have access to?*

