Discharge coordinators from RB&C 3, 5, and 6 who typically admit children who are discharged home dependent on technology will identify potential participants who meet eligibility criteria and ask if a study team member can speak with them about the study. If they agree, a study team member will talk with the parent and ask the best way to contact after the child is discharged home. Data collection would be completed following the child's discharge.

The RB&C Specialty Clinics (Pulmonary, Gastroenterology, Trach/Vent, Comprehensive Care) will identify names and contact information of patients meeting inclusion criteria. A letter describing the study and a request for the parent to contact the researcher will be sent by study staff to mothers. The letter also informs the parent that study staff will follow-up with him/her by telephone in about 1 week. This method of recruitment has been successful in the Principal Investigator's previous studies. An assent information letter for the child will

also be included with the letter sent to the mother. The parent is to give this letter to the child to read if he/she is over age 7 years and able to read it independently. If the child is over 7 years of age and is unable to read the letter independently, the mother will be asked to read it to the child. The parent will then obtain verbal assent from the child that he/she is in agreement to have the mother participate in the study. Potential participants will be contacted by telephone to assess eligibility and to determine if she is willing to participate in the study. During the telephone pre-screening interview, the nature of the study and the fact that the interview is part of a pre-screening process and does not represent enrollment in the study will be clearly explained to the subject. The questions asked during the interview do not present more than minimal risk or harm to the participants and the interview does not contain any procedures for which written consent is normally required outside of the research context according to 45 CFR 46.117 (c) 2. See attached document for pre-screening question. This question will determine if the child remains dependent on medical technology and thus determines the parent's eligibility for participation in the study.

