After confirming the child's assent and obtaining the participant's written informed consent, the participant will be assigned a code number. Mothers/fathers will be randomly assigned to one of two treatment conditions- Resourcefulness Training intervention or Attention Control using the Minim computerized method of random assignment based on parent gender, child's type of technology (mechanical ventilation or intravenous medication/nutrition, all others), race ethnicity (White non-Hispanic, all others). Data collection will take place in a private place of the mother's/father's choosing such as her/his home. The instruments should take about 50 minutes to complete at initial enrollment but thereafter it should take about 30 minutes (Table 1). After the participant has completed the self administered questionnaires, the interviewer will score the CES-D. If the total score of the CES-D exceeds the cutoff of 16 for depressive symptoms the participant will be notified and the information regarding mental health resources will be given-(see additional files). Following T1 data collection, mothers/fathers will receive either intervention or attention control protocol according to their random assignment. The RT intervention which includes instruction on maintaining a 28 day journal will take about 45-50 minutes to review with participants. At T4, one additional questionnaire, Resourcefulness Skills Scale, will be given to the Resourcefulness Training intervention group only to assess for intervention fidelity. Reminder post cards will be sent as needed. A \$25 gift card will be given following completion of questionnaires at each of four time points. Following completion and submission of all questionnaires and the RT journals, participants will be interviewed via speaker phone to determine the feasibility, acceptability and fidelity of the intervention. Telephone interviews will take place at a time convenient for the participant and will be audio-recorded. In order to aid in retention, participants will be mailed birthday cards on the parent's and child's birthdays as well as monthly postcards with an inspirational message and contact information for the study office. The **RT intervention** group will be taught RT skills and mnemonic strategies (acronyms, practice) to facilitate recall of RT skills using a web based program that includes a video approximately 32 minutes long. The 8 letters in the acronym **RESOURCE** will be used to prompt recall: **R**ely on family/friends; **E**xchange ideas with others; **S**eek professionals or experts; **O**rganize daily activities; **U**se positive self-talk; **R**eframe the situation positively; **C**hange from usual reaction; **E**xplore new ideas. Practice of RT will occur through using a personal semi-structured journal (example in other study documents) to daily record which resourcefulness skills were used that day as well as one's thoughts and feelings related to specific situations in which the resourcefulness skills were used. As intervention reminder tools mothers/fathers will be given a laminated card to keep in their journal as well as a magnet to

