
place on their refrigerator with the above 8 letter acronym RESOURCE and reminder phrases as well as the PI's name, research study office email and telephone number (See Attachment). They will also be given a brochure with a summary of the intervention. The intervention nurse will also obtain the participant's email so that an invitation can be sent to access the study RT videos on Box.com. The RT intervention group will be asked to review their RT laminated card with the RESOURCE acronym each day prior to journaling and write about any RT skills used. To assist with adherence to daily journaling, the intervention nurse will make weekly calls for 4 weeks to query for questions; reminding them to write in their journals. Mothers/fathers will be encouraged to summarize the events for any days missed. Journals will be mailed back by participants in the self-addressed, stamped envelopes provided at 4 weeks after RT to monitor adherence and review for content. The intervention nurse will also describe the use of the RTvideo and the video tape vignettes (2-3 minutes each) as examples of resourcefulness skill application during care of their technology-dependent child.

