Hair sample for cortisol level, audio recording with only subject ID number for exit interview regarding intervention for intervention group only. Questionnaires will be administered as well.

Data Analysis Plan

1. *Describe the data analysis plan, including any statistical procedures. Provide a power analysis if applicable.*
2. *If applicable, describe the primary and secondary study endpoints including safety endpoints.*

ANALYSIS. All data will be entered into UH REDCap and cleaned. We hypothesize that parents receiving the Resourcefulness Training intervention will have significant improvement in parental outcomes (psychological and physical) and family outcomes (family functioning) compared with parents in the Attention Control arm. We also hypothesize that resourcefulness will mediate the effect of the intervention on all study outcomes.

Preliminary Analyses. Exploratory data techniques will be used to examine univariate characteristics (central tendency, dispersion, and distribution) of demographics and covariates measured upon randomization in each arm. These exploratory techniques will be based on proportions (in the case of dichotomous variables) and medians and/or means (in the case of variables measured on an interval scale). Due to randomization, no formal tests of these variables will be performed because any imbalance between arms is known to be due to chance. Profile plots will also be used to describe the participant-specific (parent) and arm-specific trends for each outcome over the four time points.

Primary Analyses.

Aims 1 & 2: Analysis of the monthly rate of change in each of the parent outcomes in each arm will be estimated via linear mixed models and fit using SAS PROC MIXED.108,109 Each model will include a random intercept and slope (possibly modeled using a polynomial spline) to account for between-subject variance in each outcome over time. Conditional on these random effects, we will also explore within-subject variance in

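### Nothing stops both parents of one child from enrolling and being randomised separately, and neither the mixed models nor the mediation bootstrap has a household term

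*Combined protocol and SAP*

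**What the plan says.** Eligibility is set per parent. The main criterion in Inclusion and Exclusion Criteria is "Parents caring for a child age 16 years and younger at home who is technology-dependent", and the only exclusion listed is "Parents of children with cancer". The pre-screening described in Recruitment Methods concerns the child's equipment: "This question will determine if the child remains dependent on medical technology". It does not ask whether the other parent is already in the study. Study Design, Procedures and Timeline expects 99 women and 24 men.

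The same section makes the parent the unit of allocation: "Mothers/fathers will be randomly assigned to one of two treatment conditions", "using the Minim computerized method of random assignment based on parent gender, child's type of technology" and race/ethnicity. No household factor appears.

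RT parents receive a laminated card, a journal, a brochure, emailed video access and a magnet to "place on their refrigerator with the above 8 letter acronym RESOURCE and reminder phrases". Two of the eight taught skills are to lean on family or friends and to swap ideas with others.

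In the Data Analysis Plan each mixed model has a random intercept and slope "to account for between-subject variance in each outcome over time". The fixed effects are time, arm and stratification factors. The mediation intervals come from 1000 bootstrap samples, with no mention of resampling by household.

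On contamination, the research team's journal asks whether any has been noted. Table 1 schedules the Resourcefulness Scale at all four time points, with no restriction by arm. The separate Resourcefulness Skills Scale "will be given to the Resourcefulness Training intervention group only to assess for intervention fidelity".

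**The concern.** If a mother and father of one child both enrol, separate minimisation can put them in different arms. The control parent then shares a home with the RT reminders and with a partner who is being trained to involve family. Family functioning is the most exposed outcome. Each parent rates the same family, so a change that RT brings about in that family can appear in the control parent's score even if the control parent never looks at the materials.

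The expected bias is toward no effect. That matters here because the Background section says the study is to supply effect-size data for a larger trial, so a diluted estimate would be carried into that trial's planning. Two parents of one child may also give correlated answers, and no model allows for this.

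**Working it through.** **Inputs from the documents.** Expected enrolment is 99 women + 24 men = 123, which agrees with Number of Research Participants. At 1:1 that is 61.5 per arm. The effect is called only medium (monitoring section, item f), and no numerical alpha is given for the primary analyses.

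**Assumptions.** d = 0.5; two-sided alpha 0.05 before any Bonferroni correction; 12 or 24 couples; half of them split; carry-over c (the share of the RT effect that reaches an exposed control) of 25-100%; household ICC 0.1-0.6. Twenty-four is the maximum for mother-father couples and needs every father to have an enrolled partner. A simple difference in means stands in for the planned difference in slopes.

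**Dilution.** Exposed share s = split couples / 61.5. Diluted effect = 0.5 × (1 − s × c). Power ≈ Φ(d × √(61.5/2) − 1.96). With no exposure this is Φ(2.773 − 1.96) = 79.2%.

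| Couples | Exposed controls | c | d | Power |
|---|---|---|---|---|
| 24 | 12/61.5 = 19.5% | 25% | 0.476 | 75.1% |
| 24 | 19.5% | 50% | 0.451 | 70.6% |
| 24 | 19.5% | 100% | 0.402 | 60.7% |
| 12 | 6/61.5 = 9.8% | 25% | 0.488 | 77.2% |
| 12 | 9.8% | 50% | 0.476 | 75.1% |
| 12 | 9.8% | 100% | 0.451 | 70.6% |

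The half-split assumption is neutral. Partners share the technology factor and often race/ethnicity, so minimisation may split couples enrolled close together somewhat more often than half the time. The documents give no assignment probability, so this cannot be sized from them.

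**Ignoring the household under separate allocation.** True/assumed variance = 1 + ICC × (same-arm couples − split couples)/61.5. With 24 couples and ICC 0.5:
- all in the same arm: 1 + 0.5 × 24/61.5 = 1.195, type I error about 7.3%;
- half split: 1.00, type I error 5%;
- all split: 1 − 0.195 = 0.805, type I error about 2.9%.

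**Allocating households as units.** Design effect = 1 + (Σm²/Σm − 1) × ICC, where m is the number of enrolled parents per household. With 24 couples and 75 single parents, Σm²/Σm = (24 × 4 + 75)/123 = 1.39. The design effect is 1 + 0.39 × ICC, or 1.04 at ICC 0.1 and 1.23 at ICC 0.6. With 12 couples and 99 single parents the ratio is 147/123 = 1.195, giving 1.02 to 1.12.

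**The case against.** The strongest reply is that the premise rests on silence. No section describes a couple enrolling. Parts of the recruitment text read as if one parent per child is meant: the child assents to the mother's participation, and the caller asks whether she is willing. Recruitment also reaches well beyond the clinics, so fathers and mothers need not come from the same families. This stands as far as frequency goes: the number of couples may be zero. It does not amount to a bar.

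The size is also open to attack. Full carry-over is hard to credit when RT comprises an individual session of 45-50 minutes, a 28-day journal, weekly nurse calls and two boosters. A magnet does not deliver that. This stands too, and the lower rows of carry-over are the more credible ones. The reply is weakest for family functioning, where the route is the partner's changed behaviour rather than the materials.

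Two stronger readings are tempting and fail. A reader might infer that contamination could never be detected, because the Skills Scale goes to the RT arm only. However, the Resourcefulness Scale is scheduled for both arms at enrolment, 6 weeks, 3 months and 6 months, and staff are asked to note contamination. A reader might also infer that the missing household term inflates false positives. That happens only if couples fall mostly in the same arm. With half split it is about neutral, and with most split the test is conservative.

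**Conclusion.** The plan, followed as written, permits two parents of one child to be randomised to different arms, and it has no rule to prevent this or analyse it. The documents do not show that this will happen, or how often.

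At 24 couples with half split, about one control in five would be exposed. An assumed d of 0.5 would fall to 0.48-0.40, with the lower figure unlikely. With 12 couples the range is 0.49-0.45. The main harm is dilution toward no effect, chiefly in family functioning. The absent household term is secondary and has no fixed direction under separate allocation; it becomes necessary if households are allocated together. The gap is worth closing because it is cheap to close, not because a large loss has been shown.

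**What to change.** State in Inclusion and Exclusion Criteria and in the randomisation paragraph that one parent per child may enrol. This removes both the household contamination and the correlation. It costs one sentence and slightly fewer eligible parents.

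If both parents are to be allowed, have both consent and complete T1 before the household is allocated as one unit. Letting a later second parent follow the first parent's arm is not a good substitute. That arm would be known before the second parent consents, and partners of RT parents might join more readily than partners of controls. Joint allocation also means that parent gender as a minimisation factor must be redefined for couples.

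If couples are enrolled, record a household ID, add a household random intercept to the mixed models, resample households in the mediation bootstrap, and report the number of couples. The precision cost is a design effect of about 1.04-1.23 in the extreme 24-couple case (ICC 0.1-0.6, assumed). Joint allocation removes bias rather than adding power. At ICC 0.5 the effective size is 123/1.195 = 102.9, and power is Φ(0.5 × √(102.9/4) − 1.96) = Φ(0.576) = 71.8%, close to the 70.6% under separate allocation with 50% carry-over.

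To check for contamination, use the Resourcefulness Scale already collected in both arms at four times, comparing controls who have an RT partner with other controls. Adding the Skills Scale for controls at T4 alone, without a baseline, would add little.

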Caring for a child at home who is dependent on medical technologies such as mechanical ventilation, intravenous nutrition, feeding tubes or tracheostomies, can be a daunting task. Mothers, often the primary caregivers of technology-dependent children, not only manage the demanding care regimens and coordinate the frequent health care and therapy appointments, but must handle many other household responsibilities and perhaps outside employment. Past

research indicates that maintaining the mental health of caregivers and positive family functioning affect the chronically ill child’s growth and development.¹ Toly² found that 39.2% of mothers caring for a technology-dependent child at home (n=103) scored ≥ 16 on the Center for Epidemiological Studies- Depression Scale (CES-D) indicating high risk for clinical depression. Furthermore, 34.9% of the variance in family functioning was explained primarily by level of depressive symptoms, underscoring the impact of such symptoms.² Empirical evidence indicates that resourcefulness training (RT) is an effective cognitive-behavioral intervention that directly contributes to a decrease in negative emotions and depressive cognitions and improved functioning and health³⁻⁵ and it can be implemented on an individual basis in a variety of locales.

This pilot study will provide valuable experience in the development and testing of a RT intervention with mothers of technology-dependent children as well as provide necessary preliminary data regarding effect size for a larger, subsequent intervention study. The study results will also aid in any necessary intervention modifications based upon the feasibility, acceptability, and fidelity information gleaned from participants and interventionists.

Justification/Rationale/Significance of the Study

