The **CES-D Scale** will measure depressive symptoms.¹⁰ The 20-item interval scale ($\alpha = .85$), with responses ranging from rarely (0) to most or all of the time (3) is summed; higher scores indicate more depressive symptoms. A cut-off of 16 is used to identify those at high risk for clinical depression.

Medical Outcomes Short Form Health Survey (SF-12 v.2) is a 12-item scale that is a measure of perceived physical health status and mental health. It measures the following eight concepts: physical function, general health, bodily pain, role limitation due to physical health, bodily pain, vitality, social function, role limitation due to emotional problems and mental health. Two distinct component scores (physical, mental) are then derived. Median α for the two subscales is $> .76$.²⁷

The **Feetham Family Functioning Survey (FFFS)**, a 25-item scale ($\alpha = .85$), will assess family functioning.¹² Responses on a 7-point likert scale range from little (1) to much (7) that asks (a) how much is there now? (b) how much should there be? This provides a discrepancy score; higher scores reflect greater the dissatisfaction with family functioning.¹²

The **Demographic Characteristics Questionnaire** includes questions about the child's age, mother's/father's age, education and race. Questions regarding additional covariates such as caregiving duration (years), home health care nursing hours per week and family income are also included. Mothers/fathers will also be asked if they are willing to be contacted in at a later date should future studies be conducted. If yes, mothers/fathers will complete the section of the demographic questionnaire with address, zip codes and names and contact information of 2 persons who might know whereabouts should they move.

The **Functional Status II-Revised (FSII-R)** will assess the child's functional status.¹³ The 14-item tool ($\alpha = .86$) is administered in two parts. Part 1 asks parents about performance of the activity or behavior in the past two weeks with responses ranging from never/rarely (0) to almost always (2); Part 2 probes responses indicating poor function to determine if responses were due to illness. Higher scores indicate higher function.¹³

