answer the interview and study questions. Parents will be told that they may choose to take a break at any point during the interview. The amount of time required for participation in the study may also be viewed as an inconvenience. A potential emotional risk during the interview is that recalling information regarding their child’s course of illness and home management difficulties may make some parents uncomfortable. Participants will be told that they may withdraw from the study at any time. The interviewer will be vigilant to assess the participant’s discomfort. Participants experiencing considerable discomfort will be asked if they wish to stop the interview and will be given supportive assistance by the interviewer. The mother/father will then be given the number of United Way First Call (211) to access on call mental health professional services in their local area or Cuyahoga County 24-Hour Mental Health Crisis Information and Referral [contact]). If any participant is noted to have a level of depressive symptoms above the recognized cutoff of 16 on the Center for Epidemiological Studies (CES-D) measure she/he will be told of the findings and given an information sheet regarding accessing mental health care resources such as United Way First Help (phone 211) or the Cuyahoga County 24-Hour Mental Health Crisis Information and Referral [contact]). Any participant noted to have a score of 23 or above on the CES-D will be assessed for imminent risk of suicide by asking if they have had any thoughts of harming themselves in any way or perhaps killing themselves. If the answer to any portion of the question is “yes” the participant will be told of a concern for their safety and the necessity for the interviewer to contact the Mobile Crisis Team from the Cuyahoga County 24-Hour Mental Health Crisis, Information and Referral Hotline immediately. The risks and discomforts involved are reasonable because the risks are temporary and can be minimized by the above procedures. In addition, the discomfort is no more than what the participant might experience in her/his daily life.

**3. Describe: Procedures to decrease risk- See above
Drugs/Devices; Source Records- Not Applicable**

- Procedures performed to lessen the probability or magnitude of risks*

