Minimal risk is involved with participation in this study. Physical discomforts might involve fatigue due to the length of time (about 50 minutes) needed to answer the interview and study questions. Parents will be told that they may choose to take a break at any point during the interview. The amount of time required for participation in the study may also be viewed as an inconvenience. A potential emotional risk during the interview is that recalling information regarding their child’s course of illness and home management difficulties may make some parents uncomfortable. Participants will be told that they may withdraw from the study at any time. The interviewer will be vigilant to assess the participant’s discomfort. Participants experiencing considerable discomfort will be asked if they wish to stop the interview and will be given supportive assistance by the interviewer. The mother/father will then be given the number of United Way First Call (211) to access on call mental health professional services in their local area or Cuyahoga County 24-Hour Mental Health Crisis Information and Referral [contact]). If any participant is noted to have a level of depressive symptoms above the recognized cutoff of 16 on the Center for Epidemiological Studies (CES-D) measure she/he will be told of the findings and given an information sheet regarding accessing mental health care resources such as United Way First Help (phone 211) or the Cuyahoga County 24-Hour Mental Health Crisis Information and Referral [contact]).

Any participant noted to have a score of 23 or above on the CES-D will be assessed for imminent risk of suicide by asking if they have had any thoughts of harming themselves in any way or perhaps killing themselves. If the answer to any portion of the question is “yes” the participant will be told of a concern for their safety and the necessity for the interviewer to contact the Mobile Crisis Team from the Cuyahoga County 24-Hour Mental Health Crisis, Information and Referral Hotline immediately. The risks and discomforts involved are reasonable because the risks are temporary and can be minimized by the above procedures. In addition, the discomfort is no more than what the participant might experience in her/his daily life.

2. *If applicable, indicate which experimental procedures may have risks to the research participants that are currently unforeseeable.*

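### The CES-D notice is triggered only above 16, so a parent scoring exactly 16, the high-risk cut-off, gets no score-based notice or resource sheet

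*Combined protocol and SAP*

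**What the plan says.** The combined protocol and SAP mentions the CES-D cut-off in five places.

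- **Background (Introduction/Background).** An earlier study of mothers caring for a technology-dependent child at home is summarised by the share who "scored ≥ 16 on the Center for Epidemiological Studies- Depression Scale (CES-D) indicating high risk for clinical depression".
- **Study Design, Procedures and Timeline, Measures/Instruments.** The scale has 20 items, "with responses ranging from rarely (0) to most or all of the time (3) is summed". The text continues: "A cut-off of 16 is used to identify those at high risk for clinical depression". It does not say on which side of the line a score of 16 falls.
- **Same section, procedures text after Table 1.** The interviewer scores the CES-D once the questionnaires are finished. "If the total score of the CES-D exceeds the cutoff of 16 for depressive symptoms the participant will be notified", and information on mental health resources is given.
- **Same section, item 2 (research procedures and safety).** "If any participant is noted to have a level of depressive symptoms above the recognized cutoff of 16", that parent is told and receives an information sheet. The suicide-risk rule comes next: any participant with "a score of 23 or above on the CES-D will be assessed for imminent risk of suicide".
- **Risks to Research Participants.** Both rules are repeated in the same terms. The notice again depends on a "level of depressive symptoms above the recognized cutoff of 16 on the Center for Epidemiological Studies (CES-D) measure".

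**The concern.** Background puts a score of 16 inside the high-risk group, while the notification rule leaves 16 out. The strict form appears in all three statements of that rule, so it cannot be put down to one stray word. In two of those places it sits beside a suicide-risk threshold that is explicitly inclusive, which gives an interviewer reason to take the difference in wording literally.

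This is an operating instruction: staff compute the total and act on it, so it has to be unambiguous at the boundary. According to Table 1 the CES-D is given at enrolment, 6 weeks, 3 months and 6 months, so the boundary can arise up to four times per parent. At stake is whether a parent at the high-risk cut-off is told so and given the resource sheet because of the score. Estimation and testing are not at stake: the mixed models and mediation models in the Data Analysis Plan do not use the cut-off.

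**Working it through.** The protocol states no figure to reproduce. The check sets the rules side by side at the boundary score and counts the scores that each one covers.

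**Inputs**
- Scale: 20 items, each scored 0 to 3, summed (Measures/Instruments).
- High-risk label: score ≥ 16 (Background), with 16 named as the cut-off for that label (Measures/Instruments).
- Notice and resource sheet: score > 16 (procedures text after Table 1; item 2; Risks to Research Participants).
- Suicide-risk question: score ≥ 23 (item 2; Risks to Research Participants).

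**Is 16 attainable?** Totals run from 20 × 0 = 0 to 20 × 3 = 60 in whole numbers, which gives 60 − 0 + 1 = 61 possible values. A total of 16 is one of them.

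**The rules around the boundary**

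| Score | High risk (≥ 16) | Notice (> 16) | Suicide-risk question (≥ 23) |
|---|---|---|---|
| 15 | no | no | no |
| 16 | **yes** | **no** | no |
| 17 | yes | yes | no |
| 23 | yes | yes | yes |

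Only at 16 do the high-risk label and the notice disagree.

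**Values that trigger the notice**
- As written, 17 to 60: 60 − 17 + 1 = 44.
- With *16 or above*, 16 to 60: 60 − 16 + 1 = 45.
- Difference: 45 − 44 = 1 value, the score 16.

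**Below the suicide-risk threshold**, where the notice is the only action tied to the score:
- As written, 17 to 22: 6 values.
- With *16 or above*, 16 to 22: 7 values.

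These are counts of score values, not of parents. The Background gives 39.2% of mothers in the earlier study at 16 or more but does not say how many scored exactly 16, so no expected number of parents can be derived.

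**Does other text close the gap?** No section ties a notice or sheet to a score of exactly 16. Referral numbers are available to a parent who shows considerable discomfort in the interview (item 2; Risks to Research Participants) or who contacts staff for assistance (Adverse and Unanticipated Events). Neither route depends on the score.

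**The case against.** The best counter-argument is that no two operating rules conflict. The inclusive sign appears only in a background summary of an earlier study. The trial's own description of the instrument leaves the boundary open, and its three operating statements agree with one another. On this view the authors, who wrote an inclusive rule at 23, may have chosen a strict one for handing out a sheet. The consequence is also small: one score value, an information leaflet, other routes to help, repeated assessments and scheduled telephone contact in both arms. The procedures text also refers to additional files for the resource information. They are not available here and might state a threshold.

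Part of this stands. The inclusive reading does rest on the Background, and the consequence is slight. But the Background is the only place where the high-risk label itself has an inequality, and it concerns the same instrument, the same number and the same label. The safety text calls 16 the recognised cut-off and offers no other definition, and no reason is given for leaving 16 out. The other routes need visible distress or a request from the parent, whereas a score-based notice is useful because it reaches parents who show neither. If staff already treat 16 as included, the edit only records what they do.

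**Conclusion.** The concern holds, at low severity. Followed literally, the notification rule omits a parent who scores exactly 16, although that score meets the only directional definition of high risk in the document. The gap is 1 of 61 possible scores. Its effect is limited to the score-triggered notice and sheet, and it does not touch the suicide-risk question, the sample size or any analysis.

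Two assumptions underlie this. The first is that *exceeds* and *above* are read in their ordinary strict sense. The second is that the high-risk definition in the Background is the one the trial means when it adopts 16. If the strict threshold was deliberate, the protocol should say so and give the reason.

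**What to change.** Replace the strict wording with *a score of 16 or above* in the three statements of the notification rule: the procedures text after Table 1, item 2 of Study Design, Procedures and Timeline, and Risks to Research Participants. State *16 or above* in the CES-D description under Measures/Instruments as well. All four places would then match the Background and the inclusive form of the rule at 23. If the additional files with the resource information carry a threshold, align it too.

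The cost is four short wording edits, plus a notice and information sheet for any parent who scores exactly 16. The handling of every other score stays the same, and nothing changes in randomisation, sample size or analysis.
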